9.2.4 Study discontinuation

Boehringer Ingelheim reserves the right to discontinue the study overall or at a particular study site at any time for the following reasons:

1. Failure to meet expected enrolment goals overall or at a particular study site
2. Emergence of any effectiveness / safety information that could significantly affect continuation of the study, or any other administrative reasons
3. Violation of Good Pharmacoepidemiology Practice (GPP), the study protocol, or the contract by a study site, investigator or research collaborator, disturbing the appropriate conduct of the study

The investigator / the study site / research collaborator will be reimbursed for reasonable expenses incurred in case of study / site termination (except in case of the third reason).

9.3 VARIABLES

9.3.1 Exposures

Exposure to Spesolimab IV will be estimated as number of doses and time from the first intake date to the last intake date of the patient during the study period.

The recommended dose of Spesolimab IV is a single dose of 900 mg (2 x 450 mg/7.5 ml vials) administered as an intravenous infusion.

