- Other laboratory test results (if available)
- Safety assessment: any AEs noted
- Study completion status (if applicable)
- Investigator's overall effectiveness assessment (if applicable)

9.2.3.4 Visit 4: 24 weeks from Visit 1

After 24 weeks from Visit 1, the patient returns for a final follow-up. The following data will be collected.

- Visit date
- Any changes in the Spesolimab IV administration status
- Subsequent exposure to subcutaneous Spesolimab
- Safety assessment: any AEs noted
- Concomitant medications or non-drug therapy
- Study completion status

This visit can be conducted by [contact] Flow chart

Data points	Baseline	Follow-up 1	Follow-up 2	Follow-up 3
Visit Number	1	2	3	4
Week/s	0	1	4	24
Data release consent	X			
Diagnosis of GPP and flare ¹⁾	X			
Review of Inclusion / exclusion criteria	X			
Demographics ²⁾	X			
Medical history ³⁾	X			
Physical examination ⁴⁾	X	X	X	X
Past / concomitant medicatons or non-drug therapy ⁵⁾	X	X	X	X
Spesolimab IV administration status	X	X*	X**	X**
Supsequent exposure to subcutaneous spesolimab		X	X	X
GPPGA pustulation sub-score	X	X	X	

Data points	Baseline	Follow-up 1	Follow-up 2	Follow-up 3
Visit Number	1	2	3	4
Week/s	0	1	4	24
GPPGA score	X	X	X	
GPPASI	X ^A	X ^A	X ^A	
Pain VAS	X ^A		X ^A	
PSS	X ^A		X ^A	
CRP level	X ^A	X ^A	X ^A	
IL-36RN mutation status	X ^A			
Laboratory tests	X ^A	X ^A	X ^A	X ^A
AEs		X	X	X
Investigator's overall effectiveness assessment		X ^B	X	
Study completion		X ^B	X ^B	X

* If flare symptoms persist, an additional 900mg dose may be administered 1 week after the initial dose.

** Any changes to the Spesolimab IV administration status are collected.

^A If collected

^B If applicable

¹⁾ Date of diagnosis of GPP and this flare, average number of flares per year and family history of psoriasis

²⁾ Gender, age (year and month of birth), current pregnancy and breastfeeding status (female only), smoking status, alcohol intake status

³⁾ Within 6 months

⁴⁾ Blood pressure, pulse rate, weight (at V1 only), height (at V1 only), body temperature

⁵⁾ Within 6 months

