9.3.2 Outcomes

9.3.2.1 Primary outcomes

The primary outcomes are the safety outcomes until study completion, calculated as the incidence of:

- Adverse events (AEs)
- Adverse drug reactions (ADRs)
- Serious adverse events (SAEs)
- Serious adverse drug reactions (SADRs)
- Unexpected adverse drug reactions
- Adverse events of special interest (AESIs)
- Adverse events leading to temporary or permanent discontinuation
- Adverse events leading to death

Assessment of safety:

- AE (event name / symptom / sign)
- Onset date and end date
- Intensity (mild / moderate / severe)
- Seriousness (serious / non-serious)
- Outcome of the event (recovered / not yet recovered / sequela / fatal / unknown)
- Causality (certain / probable-likely / possible / unlikely / conditional-unclassified / unassessable-unclassifiable)
- Action taken with study drug due to AE (dose not changed / dose reduced / dose increased / drug withdrawn / not applicable)
- AESIs (systemic hypersensitivity reactions including infusion reactions and anaphylactic reaction / severe infections / opportunistic and mycobacterium tuberculosis infections)

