9.3.3 Covariates

- 1) Patient characteristics
 - Demographics: age, gender, current pregnancy status, current breastfeeding status, smoking status, alcohol intake status
 - Physical examination: height, weight, blood pressure, body temperature, pulse rate
 - Disease information: duration of disease, IL-36RN mutation status, medical history, past / concomitant medications or therapies, history and frequency of GPP flares, comorbidities (CV, hepatic or renal impairments, infection, skin diseases (i.e., plaque psoriasis)), family history
- 2) Spesolimab IV administration status: total duration of administration, total administered dose, average daily dose
- 3) Subsequent exposure to subcutaneous Spesolimab: total duration of administration, total administered dose
- 4) Patients of special investigation: pediatric population, geriatric population, pregnant women, lactating women, hepatic impairment, renal impairment
- 5) Laboratory test results
- 6) Others

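### The action-taken lists have no code for the temporary part of the discontinuation outcome; as a minor point, average daily dose can be undefined for a drug given as one or two infusions

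*Protocol*

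**What the plan says.** **Outcome and its data field.** Protocol section 9.3.2.1 lists eight primary safety outcomes, each reported as an incidence. One of them is "Adverse events leading to temporary or permanent discontinuation". The same section then fixes what is recorded for each event, including "Action taken with study drug due to AE (dose not changed / dose reduced / dose increased / drug withdrawn / not applicable". The ONIS adverse event form in Annex 8 carries the same five options, of which one is to be checked. Systemic hypersensitivity, including infusion reactions, is an adverse event of special interest (9.3.2.1 and 11.1).

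**Exposure.** Section 9.3.1 states: "Exposure to Spesolimab IV will be estimated as number of doses and time from the first intake date to the last intake date". It then says: "The recommended dose of Spesolimab IV is a single dose of 900 mg (2 x 450 mg/7.5 ml vials) administered as an intravenous infusion". A footnote to the flow chart in section 9.2.3 adds: "If flare symptoms persist, an additional 900mg dose may be administered 1 week after the initial dose". Section 9.3.3 lists the derived covariates as "Spesolimab IV administration status: total duration of administration, total administered dose, average daily dose" and gives no formula for the last of them.

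**The concern.** An outcome that covers temporary as well as permanent discontinuation needs a field that can hold both. Here only the withdrawn option corresponds to stopping. If an infusion is paused for a reaction and then resumed, none of the five options describes what happened. At stake is the count for one of the eight primary outcomes, and for the type of event (infusion reactions) that the study singles out. Section 9.7 requires the SAP to be final only before data collection ends, and a SAP cannot restore a category that was never offered at data entry.

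The exposure wording raises a smaller problem of the same kind. Duration from first to last intake and average daily dose are measures for repeated regular dosing. For a drug given once or twice they may carry no information, or rank patients in the wrong order.

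**Working it through.** **1. Outcome against codes.** No arithmetic is needed to match them.

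| Part of the outcome | Matching option in 9.3.2.1 | Matching option in Annex 8 |
|---|---|---|
| Permanent discontinuation | drug withdrawn | drug withdrawn |
| Temporary discontinuation | none | none |

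Three other sources might fill the gap:

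- Changes in IV administration status are collected at Visits 2 to 4, but nothing links a change to a particular adverse event.
- The dechallenge item in Annex 8 is tied to the event. It asks whether a dechallenge was performed and whether the event abated after the product was stopped. The protocol does not say that the outcome is derived from it, nor whether a short pause in an infusion counts as a dechallenge.
- The form refers to a free-text description of the event. No rule for deriving the outcome from it is given.

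**2. Scale of one missed case.** The enrolment target is 21 (9.5). If the safety set is 21 patients, one affected patient changes the incidence by 1/21 = 0.048, or 4.8 percentage points. The documents give no expected frequency of interruptions, so the number likely to be missed cannot be estimated.

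**3. Average daily dose.** Inputs: 900 mg per infusion (9.3.1); a possible second 900 mg after 7 days, total 1800 mg (flow chart footnote). Formula: average daily dose = total dose / number of days. The protocol states no denominator, so four were tried.

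| Denominator | One infusion (mg/day) | Two infusions (mg/day) | Ordering |
|---|---|---|---|
| (a) last minus first date, as 9.3.1 is worded | 900/0, undefined | 1800/7 = 257.1 | none possible |
| (b) last minus first date, plus 1 | 900/1 = 900 | 1800/8 = 225 | inverted |
| (c) days on which a dose was given | 900/1 = 900 | 1800/2 = 900 | tie |
| (d) 24 weeks of follow-up, 168 days | 900/168 = 5.4 | 1800/168 = 10.7 | correct |

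Under (b), twice the drug scores 225/900 = one quarter. With a gap of g days the two-infusion value is 1800/(g + 1), which falls below 900 whenever g is 2 or more; at g = 1 the two tie.

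**4. Measures that work.** Number of doses (1 against 2) and total administered dose (900 against 1800 mg) order the two patients correctly. Both are already in the protocol.

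**The case against.** On the outcome, the case for leaving the plan alone is that the measure is a composite, so temporary and permanent need not be told apart. Permanent discontinuation has a code, the dechallenge item is an event-level record of stopping, and the eCRF itself is not shown. An infusion reaction is also counted as an adverse event and as an event of special interest, whatever action is coded. All of this is fair, and it limits the damage. It does not close the gap: a composite still needs every qualifying event to be identifiable, and no rule makes the dechallenge item or the free text a source for it.

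On exposure, the objection is stronger. Section 9.3.3 only names average daily dose, and a derivation formula is commonly left to a SAP. Visit 1 collects a total daily dose, and a mean of such recorded doses would be 900 for both patients. The valid measures are already listed. What stands is that the only duration the protocol defines is 0 days for every single-infusion patient, so it is uninformative, and an average built on it does not exist.

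**Conclusion.** The main point holds: the action-taken lists in 9.3.2.1 and Annex 8 do not match the primary outcome they should supply, and its temporary part is liable to be undercounted. This assumes that the eCRF follows the list in 9.3.2.1, and that an infusion paused for an adverse event is meant to count as a temporary discontinuation. The protocol does not define that term for a drug given once or twice.

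The exposure point is minor: average daily dose is undefined on the protocol's own duration, inverted under an inclusive-day count, and tied or correctly ordered under other denominators.

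A reader might infer more than this, and the documents do not support it:

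- That the discontinuation outcome cannot be recorded at all. Its permanent part can be.
- That two infusions always rank below one. This needs an inclusive-day denominator that the protocol does not state.
- That average daily dose feeds the subgroup and regression analyses. Sections 9.7.2 and 9.7.3 base subgroups on demographics and baseline characteristics and do not list the regression covariates, so its entry is possible but not stated.
- That any dose-response reading is reversed. Number of doses and total dose are unaffected, and no dose-response analysis is specified.

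**What to change.** 1. Add one option, drug interrupted / temporarily discontinued, to the action-taken list in 9.3.2.1, to the eCRF and to Annex 8. State that the outcome is derived from interrupted plus withdrawn.
2. In 9.3.1 and 9.3.3, drop first-to-last duration and average daily dose as measures of IV exposure, and rely on number of doses and total administered dose. If an average daily dose must be kept, state its denominator.

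The cost is a few words of protocol text and one added choice on two forms. No visit, procedure or sample size changes, and no change to dosing is implied. If adverse events have already been entered, they would need a query to see whether any involved an interruption.

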9.3.2 Outcomes

9.3.2.1 Primary outcomes

The primary outcomes are the safety outcomes until study completion, calculated as the incidence of:

- Adverse events (AEs)
- Adverse drug reactions (ADRs)
- Serious adverse events (SAEs)
- Serious adverse drug reactions (SADRs)
- Unexpected adverse drug reactions
- Adverse events of special interest (AESIs)
- Adverse events leading to temporary or permanent discontinuation
- Adverse events leading to death

Assessment of safety:

- AE (event name / symptom / sign)
- Onset date and end date
- Intensity (mild / moderate / severe)
- Seriousness (serious / non-serious)
- Outcome of the event (recovered / not yet recovered / sequela / fatal / unknown)
- Causality (certain / probable-likely / possible / unlikely / conditional-unclassified / unassessable-unclassifiable)
- Action taken with study drug due to AE (dose not changed / dose reduced / dose increased / drug withdrawn / not applicable)
- AESIs (systemic hypersensitivity reactions including infusion reactions and anaphylactic reaction / severe infections / opportunistic and mycobacterium tuberculosis infections)

9.3.2.2 Secondary outcomes

The secondary outcomes are the effectiveness outcomes as follows:

- A GPPGA pustulation sub-score of 0 indicating no visible pustules at Week 1
- A GPPGA pustulation sub-score of 0 indicating no visible pustules at Week 4
- A GPPGA score of 0 or 1 at Week 1
- A GPPGA score of 0 or 1 at Week 4

The GPPGA is provided in [Annex 4](#). It is a modified the Physician's Global Assessment (PGA), a physician's assessment of psoriatic lesions, which was adapted to the evaluation of GPP patients [[R15-5200](#)]. The investigator scores the erythema, pustules, and scaling of all GPP lesions from 0 to 4. Each component is graded separately, the average is calculated, and the final GPPA is determined from this composite score. A lower score indicates a lesser severity, with 0 being clear and 1 being almost clear.

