9.2.2 Study population

9.2.2.1 Main diagnosis for study entry

Patients diagnosed with GPP in Korea

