9.2.2.2 Inclusion criteria

- ① Patients starting Spesolimab IV for the first time in accordance with the approved label in Korea (complete enumeration for the first 2 years after product launch)
- ② Patients with GPP flare
- ③ Age \geq 19 years at enrolment
- ④ Patients who have signed the data release consent form

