9.7.1.3 Number of cases to effectiveness assessment

These cases include those who signed the data release consent form to participate in this study, visited as per the study schedule, took Spesolimab IV, and were evaluated for the effectiveness.

Based on the MFDS guideline, the cases below shall be excluded from effectiveness analysis (defined below):

- a. Patients excluded from the safety analysis set listed in section [9.7.1.3](#).
- b. Patients missing information of effectiveness assessment listed in section [9.3.2.2](#).

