ANNEX 4. PHYSICIAN'S GLOBAL ASSESSMENT FOR GENERALIZED PUSTULAR PSORIASIS (GPPGA)

Erythema

- 0 = Clear: Normal or postinflammatory hyperpigmentation
- 1 = Almost Clear: Faint, diffuse pink or slight red
- 2 = Mild: Light red
- 3 = Moderate: Bright red
- 4 = Severe: Deep fiery red

Pustules

- 0 = Clear: No visible pustules
- 1 = Almost Clear: Low density occasional small discrete (non coalescent) pustules
- 2 = Mild: Moderate density grouped discrete small pustules (non coalescent)
- 3 = Moderate: High density pustules with some coalescence
- 4 = Severe: Very high density pustules with pustular lakes

Scaling/crusting

- 0 = Clear: No scaling and no crusting
- 1 = Almost Clear: Superficial focal scaling or crusting restricted to periphery of lesions
- 2 = Mild: Predominantly fine scaling or crusting
- 3 = Moderate: Moderate scaling or crusting covering most or all of lesions
- 4 = Severe: Severe scaling or crusting covering most or all lesions

PGA Score for GPP

- 0 = If mean=0 for all three components
- 1 = If $0 < \text{mean} < 1.5$
- 2 = If $1.5 \leq \text{mean} < 2.5$
- 3 = If $2.5 \leq \text{mean} < 3.5$
- 4 = If $\text{mean} \geq 3.5$

**ANNEX 5. PSORIASIS AREA AND SEVERITY INDEX FOR
GENERALIZED PUSTULAR PSORIASIS (GPPASI)****Severity****Erythema**Head 0=Clear 1=Almost clear 2=Mild 3=Moderate 4=SevereTrunk 0=Clear 1=Almost clear 2=Mild 3=Moderate 4=SevereUpper Limb 0=Clear 1=Almost clear 2=Mild 3=Moderate 4=SevereLower Limb 0=Clear 1=Almost clear 2=Mild 3=Moderate 4=Severe**Pustules**Head 0=Clear 1=Almost clear 2=Mild 3=Moderate 4=SevereTrunk 0=Clear 1=Almost clear 2=Mild 3=Moderate 4=SevereUpper Limb 0=Clear 1=Almost clear 2=Mild 3=Moderate 4=SevereLower Limb 0=Clear 1=Almost clear 2=Mild 3=Moderate 4=Severe**Scaling**Head 0=Clear 1=Almost clear 2=Mild 3=Moderate 4=SevereTrunk 0=Clear 1=Almost clear 2=Mild 3=Moderate 4=SevereUpper Limb 0=Clear 1=Almost clear 2=Mild 3=Moderate 4=SevereLower Limb 0=Clear 1=Almost clear 2=Mild 3=Moderate 4=Severe**AREA OF INVOLVEMENT**

Provide the percentage of involved area in each body region (=area affected by pustules scaling [not the area for each component separately])

Head 0=0% 1=1 to < 10% 2=10 to < 30% 3=30 to < 50% 4=50 to < 70% 5=70 to < 90% 6=90 to 100%

Trunk 0=0% 1=1 to < 10% 2=10 to < 30% 3=30 to < 50%

4=50 to < 70% 5=70 to < 90% 6=90 to 100%

Upper Limb 0=0% 1=1 to < 10% 2=10 to < 30% 3=30 to < 50%

4=50 to < 70% 5=70 to < 90% 6=90 to 100%

Lower Limb 0=0% 1=1 to < 10% 2=10 to < 30% 3=30 to < 50%

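### The GPPGA 0/1 response outcomes set no baseline condition, and a flare with visible pustules can already score GPPGA 1 at entry

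*Protocol*

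**What the plan says.** Section 9.3.2.2 lists four secondary effectiveness outcomes, two for each mandatory score. The GPPGA outcome at the first follow-up is "A GPPGA score of 0 or 1 at Week 1"; the Week 4 outcome has the same form. The other pair concerns pustules: "A GPPGA pustulation sub-score of 0 indicating no visible pustules at Week 1", again repeated at Week 4. All four are absolute states at a visit. None refers to the starting score or requires an improvement.

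On scoring, the same section says "Each component is graded separately, the average is calculated, and the final GPPA is determined from this composite score". Annex 4 gives the bands: GPPGA 0 requires a mean of zero, and GPPGA 1 covers any mean above 0 and below 1.5.

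On entry, section 9.2.2.1 gives the main diagnosis as "Patients diagnosed with GPP in Korea", and section 9.2.2.2 adds "Patients with GPP flare". Neither sets a minimum GPPGA or pustulation score. The effectiveness set in section 9.7.1.3 takes consenting patients who "visited as per the study schedule, took Spesolimab IV, and were evaluated for the effectiveness". It removes those excluded from the safety set and those with missing effectiveness data, and sets no condition on baseline severity.

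Section 8.2 states the secondary objective as evaluating changes from baseline in these scores. Both are mandatory and recorded at Visit 1 (section 9.2.3.1). Section 9.7.3 plans a paired t-test of change, separate from the response outcomes.

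**The concern.** A response outcome is informative only for patients who do not meet it at the start. If someone enters at GPPGA 1 and is still at 1 a week later, the definition as written counts a response although nothing has changed. Such a patient adds to the numerator as well as the denominator, and the rate rises with no treatment effect behind it.

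It would be natural to assume that a patient in flare cannot already be at GPPGA 0 or 1. The three-component average makes that assumption unsafe, because visible pustules can be offset by low erythema or absent scaling.

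There is also a mismatch inside the protocol. The objective speaks of change. The GPPASI, pain VAS and PSS outcomes in section 9.3.2.3 are all relative to baseline, whereas the response outcomes on the two mandatory scores are not. With a target of 21 patients, each patient moves a rate by 1/21 = 4.8 points.

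**Working it through.** The protocol states no response rate, power or precision figure, so there is none to reproduce. The check has two parts.

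**1. Can a flare with visible pustules score GPPGA 1?**

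Inputs: three components, each graded 0 to 4, and the Annex 4 bands. A mean below 1.5 is a component sum below 4.5, so GPPGA 0 or 1 means a sum of 4 or less.

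- All combinations: 5 × 5 × 5 = 125.
- Combinations scoring GPPGA 0 or 1: 35 (one scores 0, 34 score 1).
- Of these 35, pustules of grade 1 or more: 20 (ten at grade 1, six at grade 2, three at grade 3, one at grade 4).
- Of these 35, pustules of grade 2 or more: 10.

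Example: erythema 2, pustules 2, scaling 0 gives (2 + 2 + 0)/3 = 1.33, so GPPGA 1. Annex 4 describes that pustule grade as "2 = Mild: Moderate density grouped discrete small pustules (non coalescent"), which is visible disease. With all three components present, erythema 1, pustules 2, scaling 1 also gives 1.33.

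These are counts of possible score patterns, not probabilities that a patient presents with them.

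**2. How far could the reported rate move?**

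Let k of 21 patients start at GPPGA 0 or 1, let a proportion q of them be there at the visit, and let p be the response rate among the other 21 − k.

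- Rate as written = (kq + p(21 − k))/21
- Difference from p = k(q − p)/21

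The protocol gives none of k, q or p; all are assumptions. With q = 1 (all such patients stay):

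| k | p = 0.30 | p = 0.50 | p = 0.70 |
|---|---|---|---|
| 1 | +3.3 points | +2.4 | +1.4 |
| 2 | +6.7 | +4.8 | +2.9 |
| 5 | +16.7 | +11.9 | +7.1 |

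In whole patients: with k = 2 and 10 responders among the other 19, the rate among those able to respond is 10/19 = 52.6%, and the rate as written is (2 + 10)/21 = 57.1%, a difference of 4.5 points. With k = 4 and 8 of 17, 47.1% is reported as 57.1%.

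For scale, the exact 95% interval for 12/21 is 34.0% to 78.2%, and for 10/19 it is 28.9% to 75.6%.

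**The case against.** The strongest reply is that this matters little and may rarely occur. The study is a single-arm surveillance whose primary objective is safety and whose analyses are declared exploratory. Nothing in the protocol suggests that 2 or 4 of 21 patients would start at GPPGA 1. Of the ten patterns with pustules of grade 2 or more, six have no erythema at all, and only 4 of the 64 patterns with all three components present score 1. Treatment must follow the approved label, which is not shown and could narrow which flares are enrolled. The paired analysis already uses baseline, and a patient at GPPGA 1 throughout contributes zero change to it. All of this stands, and it limits the size of the point.

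A second reply is that denominators belong in the statistical analysis plan. That holds for details the protocol leaves open. Here the protocol itself states the outcome rule, and the rule has no baseline condition.

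Two stronger readings are tempting. A reader might infer that the pustulation outcomes share the fault. Annex 4 does not support this: a patient with visible pustules has a sub-score of at least 1 and so cannot meet the zero threshold at entry. A reader might also infer that patients dosed before consent, whom section 9.7.1.2 keeps in the safety set during the enumeration period, have treated scores as baselines. The protocol does not say when those scores are taken, and a score from before the infusion may be available in the medical record. That is a separate question of baseline timing. It bears on the fix, because restricting on a score taken after the infusion would remove patients who had already improved.

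**Conclusion.** The point holds for the GPPGA 0/1 outcomes at Weeks 1 and 4. As defined, they can be met without any change, because no minimum score is required at entry or in the effectiveness set and Annex 4 places some flares with visible pustules at GPPGA 1. That much follows from the protocol text alone.

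The size does not. The number of patients affected is unknown, and the 4.5-point shift for two patients is an illustration that assumes both stay at GPPGA 1. The bias is upward only if entry-level patients stay at 0 or 1 more often than the others reach it (q above p). Even then, a shift of that order is small against an interval about 44 points wide (78.2 − 34.0). The documents do not support a claim that the reported rate will be materially inflated. What they do support is that the reader of the report could not tell an entry-level score from a response. The correction is worth making because it needs no new data.

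**What to change.** In sections 9.3.2.2 and 9.7.3:

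- Report GPPGA 0/1 response at Weeks 1 and 4 among patients with a pre-infusion baseline GPPGA of 2 or more, with the all-patient rate beside it.
- Show the cross-table of baseline score by score at each visit, for GPPGA and for the pustulation sub-score. For pustulation 0 this table is enough, and no restricted rate is needed.
- List separately any patients whose only baseline score was taken after the infusion. Do not drop them as non-evaluable or apply the baseline restriction to that score.

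The cost is a few sentences and a small table, since both scores are already mandatory at Visits 1 to 3. The downside is that the restricted denominator may lose a few patients from an already small number. Keeping the all-patient rate alongside means no information is lost.
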